8.2.4. Clinical Safety Laboratory Assessments

See Appendix 2 for the list of clinical safety laboratory tests to be performed and the SoA for the timing and frequency. All protocol-required laboratory assessments, as defined in Appendix 2, must be conducted in accordance with the laboratory manual and the SoA. Unscheduled clinical laboratory measurements may be obtained at any time during the study to assess any perceived safety issues.

The investigator must review the laboratory report, document this review, and record any clinically relevant changes occurring during the study in the AE section of the CRF. Clinically significant abnormal laboratory findings are those which are not associated with the underlying disease, unless judged by the investigator to be more severe than expected for the participant's condition.

All laboratory tests with values considered clinically significantly abnormal during participation in the study or within 36 hours after the last dose of study intervention should be repeated until the values return to normal or baseline or are no longer considered clinically significant by the investigator or medical monitor.

If such values do not return to normal/baseline within a period of time judged reasonable by the investigator, the etiology should be identified and the sponsor notified.

If laboratory values from non-protocol-specified laboratory assessments performed at the institution's local laboratory require a change in participant management or are considered clinically significant by the investigator (eg, SAE or AE or dose modification), then the results must be recorded in the CRF.

Participants may undergo random urine drug testing at the discretion of the investigator. Drug testing conducted prior to dosing must be negative for participants to receive study intervention.

See Appendix 6 for suggested actions and follow-up assessments in the event of potential drug-induced liver injury.

8.2.5. Application Site Assessments

Local toleration will be assessed as specified in the SoA, by Draize scoring (Table 5) and via clinical observation.

A clinical research site staff member trained in the evaluation of skin will assess local toleration at the treatment test areas by examining the skin under standard light conditions for visible skin irritation; findings on this scale do not require reporting as an AE unless the skin response is deemed to be clinically significant by the investigator. Unscheduled Draize evaluations may be performed at any time during the study as deemed necessary by the investigator.

Scores for erythema, edema, papules, and vesicles are judged to be present if they involve 25% or more of the test area. Identifiable reaction(s) encompassing less than 25% of the test areas are to be documented as a comment rather than a score or grade. All numerical, letter grades, and superficial observations will be collected on the designated CRF.

The site staff member will be recommended to adequately describe the appearance of the skin irritation in addition to the Draize score assessment.

Table 5.	Skin Irritation	Assessment U	Using Di	raize Scoring

Definition	Score
No reaction visible	0
Trace reaction – barely perceptible pinkness	1
Mild reaction – readily visible pinkness	2
Moderate reaction – definite redness	3
Strong to severe reaction – very intense redness	4

Definition of letter grades appended to a numerical grade:

J	Burning, stinging, itching
Е	Edema – swelling, spongy feeling when palpated
Р	Papules – red, solid, pinpoint elevations, granular feeling
V	Vesicles – small elevation containing serous fluid (blister-like), diameter 5 mm or less
В	Bulla reaction – fluid-filled lesion greater than 0.5 cm in diameter
S	Spreading – evidence of the reaction beyond the test site
W	Weeping - result of a vesicular or bulla reaction - serous exudates - clear fluid oozing or
	covering test area
Ι	Induration – solid, elevated, hardened, thickening skin reaction
XC	Additional comments appear in Comments section

Definition of superficial observations appended to a numerical and/or letter grade:

G	Glazing
Y	Peeling
С	Scab, dried film of serous exudates of vesicular or bulla reaction
D	Hyperpigmentation (reddish-brown discoloration of test area)
Н	Hypopigmentation (loss of visible pigmentation at test area)
F	Fissuring – grooves in the superficial layers of the skin to glistening
R	Erosion(s)
U	Ulceration(s)
K	Scaling – flaking of skin

Photographs of dosing area are taken to document Draize scoring reaction ≥ 3 or AE at the treatment application site. These photographs are for illustrative reference only and will be used to document Draize scores ≥ 3 .Photographs will be taken in a non-identifiable manner without participants face in frame.

8.3. Adverse Events, Serious Adverse Events, and Other Safety Reporting.

The definitions of an AE and an SAE can be found in Appendix 3.

AEs may arise from symptoms or other complaints reported to the investigator by the participant (or, when appropriate, by a caregiver, surrogate, or the participant's legally authorized representative), or they may arise from clinical findings of the Investigator or other healthcare providers (clinical signs, test results, etc.).

The investigator and any qualified designees are responsible for detecting, documenting, and recording events that meet the definition of an AE or SAE and remain responsible to pursue and obtain adequate information both to determine the outcome and to assess whether the event meets the criteria for classification as an SAE or caused the participant to discontinue the study intervention (see Section 7.1).

During the active collection period as described in Section 8.3.1, each participant will be questioned about the occurrence of AEs in a nonleading manner.

In addition, the investigator may be requested by Pfizer Safety to obtain specific follow-up information in an expedited fashion.

8.3.1. Time Period and Frequency for Collecting AE and SAE Information

The time period for actively eliciting and collecting AEs and SAEs ("active collection period") for each participant begins from the time the participant provides informed consent, which is obtained before the participant's participation in the study (ie, before undergoing any study-related procedure and/or receiving study intervention), through and including a minimum of 28 calendar days after the last administration of the study intervention.

Follow-up by the investigator continues throughout and after the active collection period and until the AE or SAE or its sequelae resolve or stabilize at a level acceptable to the investigator.

For participants who are screen failures, the active collection period ends when screen failure status is determined.

If the participant withdraws from the study and also withdraws consent for the collection of future information, the active collection period ends when consent is withdrawn.

If a participant permanently discontinues or temporarily discontinues study intervention because of an AE or SAE, the AE or SAE must be recorded on the CRF and the SAE reported using the CT SAE Report Form.

Investigators are not obligated to actively seek information on AEs or SAEs after the participant has concluded study participation. However, if the investigator learns of any SAE, including a death, at any time after a participant has completed the study, and he/she considers the event to be reasonably related to the study intervention, the investigator must promptly report the SAE to Pfizer using the CT SAE Report Form.

8.3.1.1. Reporting SAEs to Pfizer Safety

All SAEs occurring in a participant during the active collection period as described in Section 8.3.1 are reported to Pfizer Safety on the CT SAE Report Form immediately upon awareness and under no circumstance should this exceed 24 hours, as indicated in Appendix 3. The investigator will submit any updated SAE data to the sponsor within 24 hours of it being available.

SAEs occurring in a participant after the active collection period has ended are reported to Pfizer Safety if the investigator becomes aware of them; at a minimum, all SAEs that the investigator believes have at least a reasonable possibility of being related to investigational product must be reported to Pfizer Safety.

8.3.1.2. Recording Nonserious AEs and SAEs on the CRF

All nonserious AEs and SAEs occurring in a participant during the active collection period, which begins after obtaining informed consent as described in Section 8.3.1, will be recorded on the AE section of the CRF.

The investigator is to record on the CRF all directly observed and all spontaneously reported AEs and SAEs reported by the participant.

Reporting of AEs and SAEs for participants who fail screening are subject to the CRF requirements as described in Section 5.4.

8.3.2. Method of Detecting AEs and SAEs

The method of recording, evaluating, and assessing causality of AEs and SAEs and the procedures for completing and transmitting SAE reports are provided in Appendix 3.

Care will be taken not to introduce bias when detecting AEs and/or SAEs. Open-ended and nonleading verbal questioning of the participant is the preferred method to inquire about AE occurrences.

8.3.3. Follow-Up of AEs and SAEs

After the initial AE or SAE report, the investigator is required to proactively follow each participant at subsequent visits/contacts. For each event, the investigator must pursue and obtain adequate information until resolution, stabilization, the event is otherwise explained, or the participant is lost to follow-up (as defined in Section 7.3).

In general, follow-up information will include a description of the event in sufficient detail to allow for a complete medical assessment of the case and independent determination of possible causality. Any information relevant to the event, such as concomitant medications and illnesses, must be provided. In the case of a participant death, a summary of available autopsy findings must be submitted as soon as possible to Pfizer Safety.

Further information on follow-up procedures is given in Appendix 3.

8.3.4. Regulatory Reporting Requirements for SAEs

Prompt notification by the investigator to the sponsor of an SAE is essential so that legal obligations and ethical responsibilities toward the safety of participants and the safety of a study intervention under clinical investigation are met.

The sponsor has a legal responsibility to notify both the local regulatory authority and other regulatory agencies about the safety of a study intervention under clinical investigation. The sponsor will comply with country-specific regulatory requirements relating to safety reporting to the regulatory authority, IRBs/ECs, and investigators.

Investigator safety reports must be prepared for SUSARs according to local regulatory requirements and sponsor policy and forwarded to investigators as necessary.

An investigator who receives SUSARs or other specific safety information (eg, summary or listing of SAEs) from the sponsor will review and then file it along with the SRSD(s) for the study and will notify the IRB/EC, if appropriate according to local requirements.

8.3.5. Environmental Exposure, Exposure During Pregnancy or Breastfeeding, and Occupational Exposure

Environmental exposure occurs when a person not enrolled in the study as a participant receives unplanned direct contact with or exposure to the study intervention. Such exposure may or may not lead to the occurrence of an AE or SAE. Persons at risk for environmental exposure include healthcare providers, family members, and others who may be exposed. An environmental exposure may include exposure during pregnancy, exposure during breastfeeding, and occupational exposure.

Any such exposure to the study intervention under study are reportable to Pfizer Safety within 24 hours of investigator awareness.

8.3.5.1. Exposure During Pregnancy

An EDP occurs if:

- A female participant is found to be pregnant while receiving or after discontinuing study intervention.
- A male participant who is receiving or has discontinued study intervention exposes a female partner prior to or around the time of conception.

- A female is found to be pregnant while being exposed or having been exposed to study intervention due to environmental exposure. Below are examples of environmental EDP:
 - A female family member or healthcare provider reports that she is pregnant after having been exposed to the study intervention by ingestion or skin contact.
 - A male family member or healthcare provider who has been exposed to the study intervention by ingestion or skin contact then exposes his female partner prior to or around the time of conception.

The investigator must report EDP to Pfizer Safety within 24 hours of the investigator's awareness, irrespective of whether an SAE has occurred. The initial information submitted should include the anticipated date of delivery (see below for information related to termination of pregnancy).

- If EDP occurs in a participant or a participant's partner, the investigator must report this information to Pfizer Safety on the CT SAE Report Form and an EDP Supplemental Form, regardless of whether an SAE has occurred. Details of the pregnancy will be collected after the start of study intervention and until 28 days after the last dose.
- If EDP occurs in the setting of environmental exposure, the investigator must report information to Pfizer Safety using the CT SAE Report Form and EDP Supplemental Form. Since the exposure information does not pertain to the participant enrolled in the study, the information is not recorded on a CRF; however, a copy of the completed CT SAE Report Form is maintained in the investigator site file.

Follow-up is conducted to obtain general information on the pregnancy and its outcome for all EDP reports with an unknown outcome. The investigator will follow the pregnancy until completion (or until pregnancy termination) and notify Pfizer Safety of the outcome as a follow-up to the initial EDP Supplemental Form. In the case of a live birth, the structural integrity of the neonate can be assessed at the time of birth. In the event of a termination, the reason(s) for terminated be specified and, if clinically possible, the structural integrity of the terminated fetus should be assessed by gross visual inspection (unless preprocedure test findings are conclusive for a congenital anomaly and the findings are reported).

Abnormal pregnancy outcomes are considered SAEs. If the outcome of the pregnancy meets the criteria for an SAE (ie, ectopic pregnancy, spontaneous abortion, intrauterine fetal demise, neonatal death, or congenital anomaly in a live-born baby, a terminated fetus, an intrauterine fetal demise, or a neonatal death), the investigator should follow the procedures for reporting SAEs. Additional information about pregnancy outcomes that are reported to Pfizer Safety as SAEs follows:

• Spontaneous abortion including miscarriage and missed abortion;

• Neonatal deaths that occur within 1 month of birth should be reported, without regard to causality, as SAEs. In addition, infant deaths after 1 month should be reported as SAEs when the investigator assesses the infant death as related or possibly related to exposure to the study intervention.

Additional information regarding the EDP may be requested by the sponsor. Further follow-up of birth outcomes will be handled on a case-by-case basis (eg, follow-up on preterm infants to identify developmental delays). In the case of paternal exposure, the investigator will provide the participant with the Pregnant Partner Release of Information Form to deliver to his partner. The investigator must document in the source documents that the participant was given the Pregnant Partner Release of Information Form to provide to his partner.

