5.3.4. Contraception

The investigator or his or her designee, in consultation with the participant, will confirm that the participant has selected an appropriate method of contraception for the individual participant and his or her partner(s) from the permitted list of contraception methods (see Appendix 4 Section 10.4) and will confirm that the participant has been instructed in its consistent and correct use. At time points indicated in the schedule of activities (SoA), the investigator or designee will inform the participant of the need to use highly effective contraception consistently and correctly and document the conversation and the participant's affirmation in the participant's chart (participants need to affirm their consistent and correct use of at least 1 of the selected methods of contraception) considering that their risk for pregnancy may have changed since the last visit. In addition, the investigator or designee will instruct the participant to call immediately if the selected contraception method is discontinued or if pregnancy is known or suspected in the participant or partner.

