10.4. Appendix 4: Contraceptive and Barrier Guidance

10.4.1. Male Participant Reproductive Inclusion Criteria

Male participants are eligible to participate if they agree to the following requirements during the intervention period and for at least 90 days after the last dose of study intervention, which corresponds to the time needed to eliminate reproductive safety risk of the study intervention(s):

• Refrain from donating sperm.

PLUS either:

• Be abstinent from heterosexual or homosexual intercourse as their preferred and usual lifestyle (abstinent on a long-term and persistent basis) and agree to remain abstinent;

OR

- Must agree to use contraception/barrier as detailed below:
 - Agree to use a male condom when engaging in any activity that allows for passage of ejaculate to another person.
- Male participants should be advised of the benefit for a female partner to use a highly effective method of contraception, as a condom may break or leak when having sexual intercourse with a WOCBP who is not currently pregnant.

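### Protocol Section 8.3.5.1 stops collecting pregnancy details 28 days after the last dose, 62 days short of the protocol's own male reproductive-risk period, and does not reconcile that stop with follow-up to outcome

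*Protocol*

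**What the plan says.** Protocol Section 8.3.5.1 (Exposure During Pregnancy, EDP) deals with pregnancies in participants and in participants' partners. It sets the collection period this way: "Details of the pregnancy will be collected after the start of study intervention and until 28 days after the last dose".

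The same section has two rules without a calendar limit:

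- On reporting: "The investigator must report EDP to Pfizer Safety within 24 hours", counted from the investigator's awareness.
- On follow-up: "Follow-up is conducted to obtain general information on the pregnancy and its outcome for all EDP reports with an unknown outcome". The investigator is to continue until the pregnancy ends and then report the outcome.

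Section 10.4.1 requires male participants to refrain from sperm donation, and to be abstinent or use condoms, during treatment and "for at least 90 days after the last dose of study intervention, which corresponds to the time needed to eliminate reproductive safety risk". It also cautions that "a condom may break or leak when having sexual intercourse with a WOCBP who is not currently pregnant".

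Under Section 10.4.2, a woman of childbearing potential cannot be enrolled. Section 5.3.4 tells participants to call the site at once "if pregnancy is known or suspected in the participant or partner", with no end date. The last scheduled contact is the phone call on Day 41±3 (Section 1.3.1).

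**The concern.** The protocol gives two different post-dose periods for the same hazard. Section 10.4.1 links its 90 days explicitly to reproductive risk. The 28 days in Section 8.3.5.1 has no reproductive rationale of its own; it matches the general adverse-event collection period in Section 8.3.1. A site or participant who reads 28 days in the pregnancy section could reasonably conclude that later partner pregnancies are no longer of interest.

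This is a first-in-human study, and embryo-fetal development studies have not been done for either compound (Section 2.1). Section 2.1 also names transfer through semen as something to be minimised. The protocol accepts that condoms can fail, so partner pregnancies inside the risk period are possible despite the contraception rules. Such a pregnancy is information the sponsor would want, and the stated window covers less than a third of the post-dose period in which it could arise.

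**Working it through.** **Inputs**

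- Last dose: Day 10, morning (Section 1.3.1, footnote j). A once-daily optional cohort also ends on Day 10 (Section 6.1.1.1).
- Collection of pregnancy details ends: last dose + 28 days (Section 8.3.5.1).
- Male reproductive-risk period ends: last dose + at least 90 days (Section 10.4.1).
- Last scheduled contact: Day 41±3, that is Day 38 to Day 44 (Section 1.3.1).
- Cohort size: about 6, randomised 4 active to 2 vehicle; two planned and two optional cohorts (Section 1.1).

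**The gap between the two periods**

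- End of collection: 10 + 28 = Day 38.
- End of risk period: 10 + 90 = Day 100 at the earliest.
- Shortfall: 100 − 38 = 62 days. This is a minimum, because 90 days is stated as a minimum.
- Share of the post-dose risk period inside the window: 28/90 = 31.1%. Outside: 62/90 = 68.9%.

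For a participant who stops dosing early, both periods start from that person's own last dose, so the difference is still 62 days.

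**Risk days after the last scheduled contact**

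- Contact on Day 38: 38 − 10 = 28 days after the last dose; 90 − 28 = 62 risk days remain.
- Contact on Day 44: 44 − 10 = 34 days after the last dose; 90 − 34 = 56 risk days remain.

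A completer's partner pregnancy in those 56 to 62 days comes to light only if someone volunteers it.

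**People to whom the 90-day rule could apply**

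- On active drug: 4 × 2 = 8 in the planned cohorts; 4 × 4 = 16 with both optional cohorts.
- In both arms, since the contraception rule does not depend on allocation: 6 × 2 = 12 and 6 × 4 = 24, before replacements.

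The documents give no sex split, so the number of men could be anywhere from 0 to those totals. They give no pregnancy rate either, so no expected number of events can be derived.

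**The two rules inside Section 8.3.5.1**

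The 28-day sentence can be read in two ways.

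1. *It limits data collection on a known pregnancy.* A pregnancy conceived during or after dosing cannot reach term by Day 38, so the follow-up-to-outcome rule in the same section could not be met for it.
2. *It limits the period in which pregnancies are identified, with follow-up separate.* The two rules are then compatible, but the identification window is 62 days shorter than the protocol's own risk period.

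The text does not say which is meant, and nothing elsewhere in the protocol or SAP settles it. The sentence needs correcting under either reading.

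**The case against.** The strongest reply is that 28 days is plainly an identification window. Section 8.3.1 already uses that scheme for adverse events: active collection for at least 28 days, with follow-up continuing afterwards. A hard stop on details of a known pregnancy would defeat the follow-up rule in nearly every case, so few would read it that way. This is fair, and the second reading is the more plausible one. But Section 8.3.1 concerns adverse events, Section 8.3.5.1 does not refer to it for this purpose, and the second reading leaves the 62-day shortfall in place.

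The next reply is that the core duties have no cut-off. The EDP definition covers a man who has already stopped treatment, the 24-hour duty runs from awareness, and the 5.3.4 instruction to call has no end date. A partner pregnancy learned of on Day 80 would still be reported and followed. This also stands, and it limits the concern considerably. What it does not supply is awareness. Participation ends with the Day 41 contact (Section 4.4), and Section 8.3.1 then releases investigators from actively seeking adverse-event information. The late-event rule in Section 8.3.1.1 helps little here: "SAEs occurring in a participant after the active collection period has ended are reported to Pfizer Safety if the investigator becomes aware of them". A partner is not a participant, and an uncomplicated pregnancy is not a serious adverse event.

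It can also be said that 69% treats every day of the 90 as equally risky. It does not measure risk. It is a share of calendar days, and the period is precautionary. Half-lives in animals were about an hour or less (Sections 2.2.2.1 and 2.2.2.2), although no human value is yet known. Vehicle recipients, who are included in the totals of 12 and 24, have no active-drug exposure.

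**Conclusion.** The concern holds, as a minor point. The stated window for pregnancy details ends at least 62 days before the male reproductive-risk period that the protocol itself sets. Its relation to the follow-up-to-outcome rule is left unstated. The shortfall falls mainly on partners of male participants. After the last scheduled contact, 56 to 62 risk days depend on volunteered reports.

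The day counts assume a completer whose last dose is on Day 10, and they take 90 days at its stated minimum. The expected risk is low: Sections 2.2.3.1 and 2.2.3.2 state that neither compound has genotoxic potential at the intended clinical doses, the study is small, and men must abstain or use condoms. No primary or secondary endpoint is affected.

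**What to change.** In Section 8.3.5.1, set the window for partners of male participants to at least 90 days after the participant's last dose. State that this is the period for identifying pregnancies, and that any reported pregnancy is followed to its outcome, as the section already requires.

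The Schedule of Activities already has a contraception check at the Day 41 contact. Use it to remind male participants that the 5.3.4 instruction to call about a partner pregnancy applies through 90 days after their own last dose, about Day 100 for completers.

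The cost is one sentence and one reminder, with no extra visit or call, and a slightly longer safety-reporting responsibility for the site and sponsor. The change does not make ascertainment active: the days after the Day 41 contact will still rely on participants coming forward. It does tell them and the site, correctly, how long that matters.
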